12.5 END OF TREATMENT

Study discontinuation refers to complete withdrawal from the study treatment. The reason for discontinuation from treatment must be recorded. Study discontinuation can be based on one or more of the following criteria:

- Adverse event(s) (physician's discretion)
- Disease progression
- Protocol violation
- Subject withdrew consent
- Lost to follow-up
- Administrative problems
- Death
- Treatment duration completed as per protocol

Furthermore, treatment ends when:

1. No return to baseline or no return to grade 1 non-hematological toxicity at any time during/after the vaccination.
2. Related SAE not otherwise categorized within the CTC v4.0 criteria (see Appendix B) but defined as severe or life threatening at any time during/after vaccination.

Based on the above, there is a differentiation between treatment withdrawal (withdraw treatment, but continue follow-up) and study drop-out (withdrawal from study e.g. unwillingness of the patient to comply with study procedures, withdraw consent, or lost to follow-up).

DCPrime must be notified and the reason(s) for treatment withdrawal/study drop-out should be documented in the eCRF; all follow-up data should also be reported.

Patients who have received at least one dose of DCP-001 who are withdrawn, or withdraw from the study will be treated according to protocol as EOT and EOT pages will be completed. If the patient does not withdraw informed consent, he/she will be requested to enter the follow up phase of the study. These patients will follow the normal schedule of the study excluding the injection of study treatment and the procedures at these visits will occur at the investigators' discretion. These patients will continue to be followed up until EOS or EOT of last patient who completed the study, whichever comes first

If the patients who are required to enter follow up do not enter follow up, for any reason, they must be requested to complete an EOT and EOS visit.

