8.4 RATIONALE FOR USING THE AML-DERIVED DC LINE DCOONE AND MODE OF ACTION

The DC-based product used in the present clinical protocol is called DCP-001, and represents the first next-generation DC vaccine. It lends itself uniquely to off-the-shelf application, and combines the immune-stimulatory features of allogeneic DC vaccines and multi-antigen vaccines. Allogeneic DCs have been reported to induce stronger antigen-specific immune responses than autologous DCs (14,15), because they trigger a broader T-cell immune repertoire, plus a broad inflammatory response. This precludes the requirement for adjuvant.

The DCP-001 vaccine formulation that will be tested in this study, has been tested in an open label, Phase I, feasibility and safety, dose escalation study (NCT01373515), without stratification or randomization, conducted in 12 elderly AML patients not eligible for additional intensification or SoC therapies. AML patients were enrolled who were either in complete remission (CR1/CR2) (n=5) or had smouldering disease (n=7). The primary objectives of the study (feasibility and safety) were achieved, with 10/12 patients completing the vaccination program. Treatment was well tolerated, and only one serious adverse events related to DCP-001 was observed. A clear-cut distinction was noted between patients with and without detectable circulating leukemic blasts during the vaccination period. Patients with circulating blasts died within 6 months post-treatment, patients without showed unusually prolonged survival (median overall survival 36 months (range 7-65) from start of vaccination treatment. Long-term survival was correlated with maintained T-cell levels and induction of multi-functional immune responses. Thus, vaccination with DCP-001 is safe and feasible in AML patients, and generates both cellular and humoral immune responses. Together with the above described characteristics of its mode of action, these clinical results from the rationale behind the intended Phase IIa.

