15.3 ADVERSE EVENT REPORTING

The investigator is responsible for monitoring the safety of patients who have enrolled in the study and for accurately documenting and reporting information as described in this section.

Patients will be instructed to report to the investigator any AE they experience. Investigators will ask about the occurrence of AEs at each visit. Investigators are required to document all AEs occurring during the clinical study, commencing with signing of the informed consent through the protocol defined end of study.

Adverse events will be scored according to the NCI Common Terminology Criteria for Adverse Events, version 4.0.

The causal relationship of AEs to study treatment will be determined by the Investigator and adjudicated by the MM. Drug-related causality will be defined as events that are definitely related, probably related, or possibly related to study drug. Events will be categorized as unrelated to study drug if they are reported as not related. The following list will be used to assist with the assessment of causality:

Definitely Related: The AE is clearly related to the investigational agent/procedure, i.e., an event that follows a reasonable temporal sequence from administration of DCP-001, follows a known or expected response pattern to the suspected drug, that is confirmed by improvement on stopping and reappearance of the event on repeated exposure and that could not be reasonably explained by the known characteristics of the subject's clinical state.

Probably related: When there is a temporal relationship to the study drug administration, significant symptoms abate upon discontinuation of DCP-001 and there is a reasonable explanation based on known characteristics of the study drug and there is no clear association with pre-existing disease or therapy, intercurrent illness, concurrent therapy, or other factor(s).

Possibly related: An event that follows a reasonable temporal sequence from the administration of DCP-001, follows a known or expected response pattern to the suspected drug, but that could readily have been produced by a number of other factors.

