Not related: The AE is clearly not related to the investigational agent/procedure. Another cause of the event is most plausible; and/or a clinically plausible temporal sequence is inconsistent with the onset of the event and the study medication administration; and/or a causal relationship is considered biologically implausible. Concurrent illness, concurrent medication or other known cause is clearly responsible for the AE.

The action taken with study treatment will be reported according to the following options: Dose not changed, Dose reduced, Drug interrupted, Drug withdrawn, Not applicable, and Unknown.

In accordance with international regulatory requirements, there is a separate reporting system for SAEs.

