15.6 EXPECTED SIDE EFFECTS OF STUDY MEDICATION

Results from numerous clinical trials with DCs indicate that DC-based immunotherapy is safe and well-tolerated. There may be a slight discomfort due to the local skin reaction following injection.

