15.8 DATA SAFETY MONITORING BOARD

The DSMB will meet per the DSMB Charter.

The primary responsibility of the Data Safety Monitoring Board (DSMB) is to ensure safety of patients prior to administration of the next vaccination of DCP-001. The DSMB consist of qualified experts in the disease area but are otherwise independent of the study. In case of doubt regarding the interpretation of any AEs, responsible investigators will on the shortest notice report the issue to the medical monitor who will consult with the DSMB, at least in case of any SAE determined to be related to DCP-001 administration. The DSMB will review each SAE and all severe laboratory abnormalities as rapidly as possible and provide advice whether the study can reasonably continue. Other AEs, including laboratory data which may indicate toxicity, will be reviewed periodically. The DSMB will discuss, analyse on the issue, and report to the investigator and the sponsor. Ultimately the sponsor will decide whether the study should be discontinued (section 14.6).

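### Mandatory stopping rule 2 in Section 12.5 omits related severe or life-threatening SAEs that CTC v4.0 categorises, so one that resolves triggers no mandatory stop for that patient

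*Protocol*

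**What the plan says.** Section 12.5 of the protocol has two tiers. The first is a permissive list of reasons on which discontinuation can be based; it includes adverse events, at the physician's discretion. The second tier is mandatory and states when treatment ends:

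- Rule 1: "No return to baseline or no return to grade 1 non-hematological toxicity at any time during/after the vaccination".
- Rule 2: "Related SAE not otherwise categorized within the CTC v4.0 criteria (see Appendix B) but defined as severe or life threatening", at any time during or after vaccination.

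Section 15.3 sets the grading system: "Adverse events will be scored according to the NCI Common Terminology Criteria for Adverse Events, version 4.0".

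Section 15.8 makes patient safety before the next vaccination the primary responsibility of the DSMB. The medical monitor consults it "at least in case of any SAE determined to be related to DCP-001 administration". It also reviews each SAE as rapidly as possible, in order to "provide advice whether the study can reasonably continue". The sponsor takes the final decision on discontinuing the study.

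**The concern.** Rule 2 is the only mandatory rule tied to the severity of a related SAE, and its qualifier removes the events that the trial's own grading system categorises. The wording reads like a residual clause meant to follow a main rule for categorised events, but no such main rule appears. That origin is an inference from the wording; the effect does not depend on it.

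Safety and tolerability is a primary objective (Section 9.1.1). Patients are due six doses, the first four at two-week intervals (Section 12.3). Section 12.4 requires at least 60 minutes of observation after each vaccination for immediate reactions, and exclusion criterion 15 in Section 11.3 bars anyone with a history of hypersensitivity to the product. An acute reaction can settle within two weeks. If it is related, life threatening, categorised by CTC v4.0 and resolved by the next visit, no mandatory rule stops the next dose. An uncategorised reaction of the same severity would end treatment. The protocol gives no reason for the difference, and sites may handle like cases differently.

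**Working it through.** The protocol states no figure on this point, so the check is to apply the two rules to each kind of case.

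**Inputs.** Rules 1 and 2 and the discretionary list come from Section 12.5, the grading system from Section 15.3. All cases considered are related SAEs that are severe or life threatening. They are split by categorised in CTC v4.0 (yes/no), haematological (yes/no) and resolved (yes/no): 2 × 2 × 2 = 8 case types. Resolved means back to baseline; unresolved means still above both baseline and grade 1.

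**Two readings of rule 1.** On the narrow reading, the restriction to non-haematological toxicity governs both halves of the rule. On the broad reading, failure to return to baseline stands alone and covers any toxicity. The narrow reading is the more natural one.

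| Case types | Rule 2 | Rule 1, narrow | Rule 1, broad |
|---|---|---|---|
| Not categorised (4 types) | stops all 4 | not needed | not needed |
| Categorised, non-haematological, unresolved | no | stops | stops |
| Categorised, haematological, unresolved | no | no | stops |
| Categorised, non-haematological, resolved | no | no | no |
| Categorised, haematological, resolved | no | no | no |

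**Count.** Narrow reading: 4 + 1 = 5 of 8 stopped. Broad reading: 4 + 2 = 6 of 8 stopped. The 2 resolved, categorised types are missed on both.

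**Intermediate case.** For an event that settles at grade 1 above a baseline of 0, the outcome depends on whether rule 1 requires return to baseline or accepts grade 1. Full return to baseline avoids that question.

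**Search for another mandatory stop.** Section 12.5.1 deals with follow-up and replacement. Section 14.5 allows the sponsor to terminate the study. Sections 15.3 and 15.5 deal with grading, causality and reporting, and Section 15.7 with follow-up of events. Section 15.8 gives the DSMB review and advice. None of them ends an individual patient's treatment automatically.

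**With the qualifier deleted.** Rule 2 stops all 8 types.

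**The case against.** The strongest reply is that the patient is already protected. The physician may stop treatment for any adverse event. The DSMB is consulted on at least every related SAE, reviews each SAE rapidly and has safety before the next vaccination as its first duty. In an open-label trial of 20 patients, leaving resolved events to case-by-case judgement can be defended. Section 9.2.4 also refers to a DSMB charter and a safety plan, neither of which is available here, and only the heading of Appendix B can be seen. A patient-level rule in one of these cannot be excluded.

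Much of this stands, and it lowers the weight of the point. It does not explain why the protocol, having chosen mandatory rules, applies one to uncategorised events and not to categorised events of equal severity. The advice in Section 15.8 is framed around whether the study continues, and its remit before the next dose sets no stop for a patient.

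Several stronger readings are tempting but unsupported:

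- A reader might infer that no haematological event is covered. The unresolved one is covered on the broad reading of rule 1.
- A reader might use the Phase I report, that "only one serious adverse events related to DCP-001 was observed" among 12 patients, to estimate how often the gap would matter. That counts any related SAE; the text available does not give its grade, category or recovery.
- A reader might take the adverse event form's options for action taken, "Dose not changed, Dose reduced, Drug interrupted, Drug withdrawn, Not applicable, and Unknown", as permission to re-vaccinate. They are reporting choices for all adverse events and authorise nothing.
- A reader might infer that rule 1, taken literally, removes a patient with a lingering grade 1 skin reaction and so costs one of ten in a dose group. That requires a strained reading, and Section 12.5 separates treatment withdrawal from study drop-out.

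**Conclusion.** The point holds in a limited form. A related severe or life-threatening SAE that CTC v4.0 categorises and that returns to baseline before the next dose meets neither mandatory rule in Section 12.5, on either reading of rule 1. Only physician discretion and DSMB review then apply. Whether an unresolved haematological event is also missed depends on the reading.

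The size is 2 of 8 case types missed for certain and 3 of 8 on the narrow reading. This counts kinds of event and says nothing about how often they occur. The conclusion assumes that the qualifier means what it says and that no separate stop exists in the charter, the safety plan or the body of Appendix B. It does not show that patients lack oversight. It is a cheap improvement to the protocol.

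**What to change.** In rule 2 of Section 12.5, strike the reference to events that CTC v4.0 does not otherwise categorise, together with the pointer to Appendix B and the linking word 'but'. Rule 2 then ends treatment for any related SAE that is severe or life threatening, at any time during or after vaccination, whether or not CTC v4.0 categorises it and whether or not it resolves. Leave rule 1 as it is: a recovery deadline there, without a condition of relatedness, would end treatment for unrelated toxicity.

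The cost is an amendment to one sentence, with no extra visits or data. The downside is possibly a few more mandatory stops in place of case-by-case judgement. Those patients lose their remaining doses but not their place in the trial. Unless they withdraw consent, Section 12.5 asks them to continue the visit schedule without injections, with procedures at the investigator's discretion. Under Section 16.2.1 they remain in the Safety Population, and in the Immunogenicity Population if any follow-up immune data are recorded.

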6 SYNOPSIS

| | |
|--|---|
| Name of Sponsor/Company: DCprime bv | |
| Name of Investigational Product: DCP-001 | |
| Name of Active Ingredient: The active ingredient consists of allogeneic human dendritic cells (DCs) derived from the CD34+ progenitor AML cell line, DCOne. These DCs endogenously express several AML specific leukemia associated antigens (LAA) that include WT1, MUC1, PRAME and RHAMM. | |
| Title of Study: Allogeneic Dendritic cell Vaccination in AML oNgoing Clinical Evaluation II | |
| Short Study Title (acronym): ADVANCE II | |
| Study center(s): Approximately 3-5 sites Countries: Netherlands, Germany | |
| Coordinating Investigators: [name]. [name] | |
| Studied period (years): Recruitment time: 12 - 18 months. Treatment time: 4.5 months Follow up time: 12 months after the last patient receives the last biweekly (4 th) vaccination. Total Study duration: approximately 34 months | Phase of development: IIa, Proof of Concept |
| Rationale: Immunotherapy offers promise in AML and has created opportunities for improved outcomes. Dendritic cell (DC)-based immunotherapy has shown to be a promising strategy for the elimination of minimal residual disease (MRD) in patients with acute myeloid leukemia (AML). DCP-001 is an allogeneic dendritic cell based immunotherapeutic vaccine that expresses a number of tumour antigens that are expressed in AML and have shown clinical results when applied as peptide vaccines or loaded onto patient derived DC. Evidence for DCP-001 mediated safety, feasibility and immunological responses have been demonstrated in a Phase I study; the current study aims to generate evidence for clinical efficacy. | |
| Objectives: Primary: 
 • To assess the effect of DCP-001 on MRD. MRD will be measured by flow cytometry pre and post vaccination as a surrogate marker for established clinical endpoints in AML. • To assess the effect of DCP-001 on immune responses in AML patients in first complete remission (CR1) and persistent MRD. • To document safety and tolerability. | |

| |
|---|

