| 
Secondary:
 
• To identify surrogate (immunological) markers that might correlate with clinical outcome.• To quantify any lag time between initiation of treatment & onset of effect.• To determine the effect of DCP-001 on Time to Relapse (TTR).• To determine the effect of DCP-001 on Overall Survival (OS) during the study.• To document the difference between the two vaccination regimens based on MRD outcome and immunological parameters. |
| 
Methodology:
 
International, multicentre, open-label proof of concept study without randomization and stratification. Two different dose groups are included. Group 1 consists of 10 patients that will receive 25E6 DCP-001 cells per vaccination with two additional booster vaccinations of 10E6 cells. Group 2 consists of 10 patients who will receive 50E6 DCP-001 cells per vaccination with two additional booster vaccinations of 10E6 cells.
 
Patients will be screened for eligibility for the study and evaluated at baseline, at each vaccination visit and every 8 weeks during follow up. Each patient will be followed up for 12 months after the 4th vaccination. Sera and cell samples (blood and bone marrow) will be collected when indicated for efficacy (MRD evaluation) and immune response monitoring.
 |
| 
Number of patients (planned):
 
No less than 20 patients are planned for participation
 |
| 
MRD assessment:
 
MRD will be determined at start of the vaccination, prior to the first boosting vaccination, after the last boosting and a final MRD assessment will be performed 100 days after receiving the last boost (day 224). MRD will be determined with multi-parametric flow cytometry. Flow cytometric MRD is based on leukaemia associated phenotype (LAP) that will be established at diagnosis and at specified time points post-vaccination. MRD will be reported as a percentage of the whole white blood cell compartment in complete remission, according to standardized protocols. Assessment of MRD will be performed by a central lab (VUmc).
 |

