| 
Duration of treatment:
 
4 vaccinations at biweekly intervals, followed by two booster vaccinations 8 and 12 weeks after the 4th (week 6) vaccination. Total treatment duration 18 weeks.
 |
| 
Reference therapy, dosage and mode of administration:
 
N.A.
 |
| 
Criteria for evaluation:
 
1. Any change in MRD (flow cytometric) as compared to baseline MRD2. Any change in immunoreactivity (specific and non-specific) as compared to baseline. |
| 
Safety endpoints:
 
1. Treatment emergent adverse events (TEAEs) will be collected in the first 48 hours after the first vaccination to determine (acute) toxicity due to intradermal injection.2. All TEAEs will be collected during the study for each patient and the grade of toxicity using Common Terminology Criteria for Adverse Events (CTCAE V4) and relationship to product determined.3. A Data Safety Monitoring Board (DSMB) will meet after every 5 patients treated to evaluate safety; written reports will be made of each meeting.4. All Serious Adverse Events (SAEs) will be reported by the investigator within 24 hours of first knowledge. All SAEs will be reported in a timely manner to the appropriate regulatory body, consistent with existing regulations. Information on relevant SAEs will be disseminated between sites in a timely manner.5. The safety and efficacy databases will include only the subjects included in study and received a least one vaccination. |

Statistical Methods:

Sample Size Assumptions: The planned sample size of 20 evaluable subjects will be distributed 1:1 with 10 subjects each in Group 1 - 25E6 DCP-001 cells per vaccination, and Group 2 - 50E6 DCP-001 cells per vaccination. Additional subjects may be enrolled to ensure that 20 evaluable subjects complete the study. The sample size is based on practical considerations, rather than strict sample size statistical considerations with a desired power for a pre-specified difference.

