7 FLOW CHART AND SCHEDULE OF ASSESSMENTS

Table 1: Flowchart and assessment schedule

| | Screening | Baseline wk 0 | wk 0 | wk 2 | wk 4 | wk 6 | wk 6 | wk 11 | wk 14 | wk 18 | wk 18 | wk 20 | wk 32 | FU ¹ +8 weeks | End of Study ² (Final FU Visit) |
|--|-----------|--------------------|----------------|-----------------|-----------------|-----------------|-----------------|-----------------|-----------------|------------------|------------------|------------------|------------------|--------------------------------|---|
| days | -28 | 0 | 2 ⁷ | 14 ⁸ | 28 ⁸ | 42 ⁸ | 44 ⁷ | 77 ⁸ | 98 ⁸ | 126 ⁸ | 128 ⁷ | 140 ⁸ | 224 ⁸ | | |
| Visit No. | 1 | 2 | 3 | 4 | 5 | 6 | 7 | 8 | 9 | 10 | 11 | 12 | 13 | 14-17 | 18 |
| Informed consent | √ | | | | | | | | | | | | | | |
| Inclusion/exclusion criteria | √ | | | | | | | | | | | | | | |
| Demographics | √ | | | | | | | | | | | | | | |
| Medical History | √ | | | | | | | | | | | | | | |
| Physical examination | √ | √ | | √ | √ | √ | | √ | √ | √ | | √ | √ | √ | √ |
| ECOG | √ | √ | | √ | √ | √ | | √ | √ | √ | | √ | √ | √ | √ |
| HLA Typing ¹¹ | √ | | | | | | | | | | | | | | |
| Vital signs | √ | √ ³ | | √ | √ | √ | | √ | √ | √ | | √ | √ | √ | √ |
| ECG, X-thorax | √ | | | | | | | | | | | | | | |
| Haematology ⁴ | √ | √ ³ | | √ | √ | √ | | | √ | √ | | √ | √ | √ | √ |
| Biochemistry ^{5, 13} | √ | √ ^{3, 13} | | √ | √ | √ | | | √ | √ | | √ | √ | √ | √ |
| Urine analysis ¹⁰ | √ | | | | | | | | | | | | | | √ |
| Viral tests (HIV, Hepatitis B and C) ¹² | √ | | | | | | | | | | | | | | |
| MRD assessment (BM aspirate) | | √ | | | | | | | √ | | | √ | √ | | |
| DCP-001 Vaccination | | √ | | √ | √ | √ | | | √ | √ | | | | | |
| Immunomonitoring | | √ | √ | | | | √ | √ | | | √ | √ | √ | | |
| Skin biopsy ⁹ | | | √ | | | | √ | | | | √ | | | | |
| End of treatment | | | | | | | | | | | | | √ | | |
| End of study | | | | | | | | | | | | | | | √ |
| Prior and Concomitant medication | √ | √ | √ | √ | √ | √ | √ | √ | √ | √ | √ | √ | √ | √ | √ |
| Adverse event reporting ⁶ | | √ | √ | √ | √ | √ | √ | √ | √ | √ | √ | √ | √ | √ | √ |

- 1) Follow up visits on wk 40, 48 and 56
- 2) End of study visit (last FU visit) will be performed 12 months after 4th vaccination, or, no more than 2 weeks after last treatment received if a patient goes off study before week 32
- 3) If baseline assessment is within 7 days of first vaccination and if results meet the stated eligibility criteria, these assessments need not to be repeated on day 0

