12.2 METHOD OF ASSIGNING SUBJECTS TO TREATMENT GROUPS

First 10 patients will receive the lowest dose (25E6cells/vaccination), the 2nd 10 patients will receive the high dose (50E6cells/vaccination).

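### Section 12.5 can end a withdrawn patient's follow-up at another patient's end of treatment, contradicting the 12-month follow-up promised to every patient and falling mainly on the high-dose group

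*Protocol*

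**What the plan says.** Section 12.5 separates stopping treatment while continuing follow-up from dropping out of the study. Those who stop treatment and keep consent stay on the normal visit schedule without injections, with procedures at the investigator's discretion. Their follow-up then ends as follows: "These patients will continue to be followed up until EOS or EOT of last patient who completed the study, whichever comes first".

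The Synopsis makes no such exception: "Each patient will be followed up for 12 months after the 4th vaccination". Table 1, footnote 2, agrees for the final visit: "End of study visit (last FU visit) will be performed 12 months after 4th vaccination".

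Three other statements determine how the Section 12.5 limit works:

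- Allocation (Section 12.2) follows enrolment order: "First 10 patients will receive the lowest dose (25E6cells/vaccination), the 2nd 10 patients will receive the high dose (50E6cells/vaccination").
- The Synopsis gives "Recruitment time: 12 - 18 months".
- EOT has two possible days. The Table 1 row "End of treatment" is ticked only at week 32 (Day 224), and Section 14.1 lists Day 224 under the treatment period. The Synopsis gives "Total treatment duration 18 weeks", which is Day 126.

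**The concern.** A follow-up limit should run on the patient's own time or apply to everyone at one data cut-off. This one does neither. It applies only to patients who stopped treatment, and its date depends on when someone else finishes. The reasons for stopping listed in Section 12.5 include disease progression and adverse events, so the patients affected are selected on prognosis.

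Because the high dose is given only to the second ten patients, those enrolled close to the last completer are mostly high-dose. Time to relapse and overall survival are secondary objectives (Section 9.1.2), and Section 16.2 presents summaries by treatment group. With 10 patients per group, a few follow-up times shortened for reasons of enrolment order can alter a Kaplan-Meier curve in one group and not the other. Follow-up that was never collected cannot be restored in the analysis.

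**Working it through.** **Inputs.** 4th vaccination on Day 42; own EOS on Day 42 + 365 = 407; EOT on Day 224 (Table 1) or Day 126 (18 weeks); recruitment of 12 or 18 months; patients 1-10 low dose, 11-20 high dose. EOS in the Section 12.5 sentence is taken as the patient's own.

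**The plan's own figure.** The protocol gives no figure for this rule. The nearest is the total duration of about 34 months: 18 + 4.5 + 12 = 34.5, which agrees. A patient enrolled at month 18 reaches Day 407 at 18 + 42/30.44 + 12 = 31.4 months, inside that duration.

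**Rule.** A patient enrolled at time t is cut at T + EOT day, where T is the enrolment date of the last completer. The cut precedes the patient's own EOS when T − t < 407 − EOT day:

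- EOT on Day 224: 407 − 224 = 183 days.
- EOT on Day 126: 407 − 126 = 281 days.

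It precedes the patient's own Day 224 when T − t < 224 − EOT day. That is 0 days for the first reading (only patients enrolled after the last completer) and 98 days for the second.

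**Even accrual, patient 20 the last completer.** Spacing is 12 × 30.44/19 = 19.2 days or 18 × 30.44/19 = 28.8 days. The table shows which patients would be cut if they withdrew.

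| Recruitment | EOT day | Low-dose, before own EOS | High-dose, before own EOS | Before own Day 224 (beyond the 3-day window) |
|---|---|---|---|---|
| 12 months | 224 | none | 11-19 (9) | none |
| 18 months | 224 | none | 14-19 (6) | none |
| 12 months | 126 | 6-10 (5) | 11-19 (9) | 16-19 |
| 18 months | 126 | none | 11-19 (9) | 17-19 |

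With EOT on Day 224, follow-up available to high-dose patients 11-19, were they to withdraw, averages 224 + 5 × 19.2 = 320 days (12 months). For 18 months it averages 352 days, capping each patient at 407. It is 407 days for low-dose patients.

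**Random accrual.** 40,000 simulated trials, uniform enrolment, withdrawal probability 10%, 16.7% (the Phase I rate, 2 of 12 not completing) or 30%, no replacement. Ranges are over the three rates.

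| Recruitment | EOT day | Withdrawn low-dose cut before EOS | Withdrawn high-dose cut before EOS | High-dose share of cuts | Withdrawn high-dose cut before Day 224 |
|---|---|---|---|---|---|
| 12 months | 224 | 16-18% | 96% | 84-86% | 10-13% |
| 18 months | 224 | 2-3% | 76-79% | 97-98% | 10-13% |
| 12 months | 126 | 65-68% | 100% | about 60% | 63-65% |
| 18 months | 126 | 17-20% | 96-97% | 83-85% | 46-49% |

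Low-dose cuts before Day 224 are zero with EOT on Day 224 and under 1% otherwise.

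**In patients.** At 16.7% withdrawal, 10 × 0.167 = 1.67 withdrawals are expected per group. With EOT on Day 224, those cut before EOS number:

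- High dose: 1.67 × 0.958 = 1.6 (12 months) or 1.67 × 0.768 = 1.3 (18 months).
- Low dose: 1.67 × 0.164 = 0.3 or 1.67 × 0.019 = 0.03.

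Cuts before Day 224 are about 1.67 × 0.11 = 0.2 high-dose patients.

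**The case against.** The strongest reply is that Sections 6 and 16.2 limit the described analysis to data up to Day 224. With EOT as in Table 1, nobody enrolled on or before the last completer is cut before that day. No 12-month survival endpoint is named, the between-regimen objective covers MRD and immunological parameters only, and the plan is descriptive. This stands, and it places the harm in the longer survival and relapse follow-up that the protocol collects beyond Day 224.

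Replacement also helps. Section 12.5.1 replaces patients who stop within 2 months for reasons other than adverse drug reactions, and extra enrolment is allowed so that 20 evaluable patients complete. A later-enrolled completer moves the cut later. The simulation ignores this, so its Day 224 losses are somewhat high.

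Other rules already shorten follow-up in both groups. Section 14.1 ends visits at disease progression, Table 1 footnote 2 brings the final visit forward for patients off study before week 32, and procedures after withdrawal are discretionary. A patient withdrawn for progression has usually already supplied a relapse time, so time to relapse loses little there. These points stand too, but none of these rules is tied to enrolment order, so none creates the dose imbalance. Footnote 2 concerns patients off study, whom Section 12.5 distinguishes from those who only stop treatment.

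A reader might infer that the rule generally costs the final MRD result, or that it affects the high-dose group alone. The documents support neither. Under the Table 1 EOT, Day 224 is lost only for unreplaced withdrawn patients enrolled after the last completer. The absence of low-dose cuts depends on even accrual: with 12-month recruitment, patient 10 clears the 183-day line by only 10 × 19.2 − 183 = 9 days.

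**Conclusion.** The contradiction is real: Section 12.5 gives treatment-withdrawn patients a shorter and externally set follow-up than the Synopsis gives every patient. Sequential dose groups make the shortfall mainly high-dose. With EOT on Day 224 the exposed patients number 0 low-dose against 9 or 6 high-dose under even accrual, and about 85% or 97-98% of cuts are high-dose under random accrual, for 12 or 18 months of recruitment. If EOT means week 18, 12-month recruitment exposes 5 low-dose and 9 high-dose patients, and late high-dose patients can also lose Day 224.

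In absolute terms this is one or two high-dose patients at the Phase I non-completion rate. The accrual pattern and withdrawal rate are assumptions. The direction of the imbalance follows from sequential filling. The loss is to overall survival and time-to-relapse follow-up after Day 224. The documents do not support calling it a defect of the primary MRD analysis or of a 12-month survival endpoint.

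**What to change.** In Section 12.5, remove the limit tied to the last completer's EOT, together with the condition that the earlier date applies. State that withdrawn patients who keep consent are followed on their own schedule to the same 12-month point as other patients, counted from the actual or planned date of the 4th vaccination, at least for relapse and survival status.

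That deletion alone is not enough. The same amendment should:

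- define EOT once, since Table 1 and the Synopsis treatment duration point to different days;
- define EOS once and say whose EOS is meant, since Section 14.1 heads the final visit as 12 months after the last vaccination whereas Table 1 counts from the 4th;
- reconcile Section 12.5 with the Synopsis, Table 1 footnote 2 and the stop at progression in Section 14.1, and say which data are still collected once visits stop.

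The cost is a few extra follow-up contacts for a small number of patients. Almost all fall within the planned study period, because the study already stays open until 12 months after the last patient's 4th vaccination.
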